## 4 Study Design

### 4.1 Overall Design

This is a randomized, double blind, cross-over study of the combination of atomoxetine and oxybutynin in children with DS and OSA documented by polysomnography (PSG).

Approximately 27 participants will be randomized in the study. Participants will receive high dose ato-oxy for four weeks as well as low dose ato-oxy for four weeks in random order. During the high dose ato-oxy period, participants will take 5 mg oxybutynin and 0.5 mg/kg/day (max 40 mg) atomoxetine nightly for one week. Atomoxetine dose will then be increased to 1.2 mg/kg/day (max 80 mg) and oxybutynin will remain at 5 mg. During the low dose ato-oxy period, participants will take 5 mg oxybutynin and 0.5 mg/kg/day (max 40 mg) atomoxetine nightly. Overall study duration will be 10-15 weeks. Dosing of the study treatment will occur approximately 30 minutes prior to bedtime. Participants who withdraw from the study will not be replaced.

Study participants will undergo eligibility screening that will include an initial screening to determine whether non- PSG enrollment criteria are met, followed by a 1 night in-lab PSG and health-related quality of life assessment for participants who qualify based on non-PSG criteria. For participants who are eligible and enroll in the study, the screening PSG night will serve as the baseline measure for apnea hypopnea index (AHI) and other PSG endpoints. On the final night of dosing for both high dose ato-oxy and low dose ato-oxy, participants will return for inpatient PSG and health-related quality of life assessment. The primary efficacy endpoint is the change in obstructive AHI from baseline (high dose ato-oxy vs. low dose ato-oxy).

**Figure 2:** Overview of Study Design

Participants will be randomized to either high dose ato-oxy or low dose ato-oxy at baseline. Polysomnography (PSG) and health-related quality of life (HR-QOL) assessment will be performed after four weeks of treatment. Participants will then take no drug for two weeks, then take the alternate treatment for four weeks with repeat PSG and HR-QOL assessment at the end of therapy.

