**Exclusion Criteria based on baseline polysomnography (prior to randomization)**

1. Hypoxemia independent of respiratory events on polysomnography ( $\geq 5$  minutes with oxygen saturation <90%)

2. Presence of central sleep apnea on polysomnography (central AHI  $\geq 5$ )

3. Absence of OSA defined as total AHI <5

[figure not shown]
Children with or without history of prior adenotonsillectomy will be enrolled as long as they have current OSA (defined as AHI  $>5$ ) on baseline polysomnography. Children who are initially excluded due to tonsillar hypertrophy will be eligible to participate in the study if they have persistent OSA after adenotonsillectomy. Additionally, children will be eligible regardless of body mass index (BMI), as the prior study of ato-oxy in adults included participants with

significant obesity, and ato-oxy was demonstrated to be effective in adults with a BMI as high as 40 (Taranto-Montemurro, Messineo et al. 2018).

Pediatric OSA is defined in the International Classification of Sleep Disorders (3rd edition) by an obstructive AHI  $\geq 1$ . While we considered using this as our inclusion criteria to maximize generalizability to all children with OSA, we decided against this approach for several reasons.

First, half of our study population will be adolescents, and based on American Academy of Sleep Medicine guidance in the current polysomnography scoring manual, use of the adult definition of OSA (total AHI  $\geq 5$ ) may be more appropriate in adolescents.

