## 9 Statistical Considerations

### 9.1 Statistical Hypotheses

The null hypothesis is no difference in change from baseline in obstructive AHI in the high dose ato-oxy study period compared to the low dose ato-oxy study period.

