### 9.2 Sample Size Determination

Under the mixed effects model setting the primary analysis for comparing high dose ato-oxy with low dose ato-oxy is reduced to a two-sample t test with a common variance of  $\sigma^2/2$ , where  $\sigma^2$  is the residual variance (Hills and Armitage 2004). Based on prior research with a sample size of 20 subjects, a median change of -15.9 in AHI with interquartile range (-35.9, -7.3) was observed with a p-value of <0.001 (effect size [Cohen's d] of 1.4) (Taranto-Montemurro, Messineo et al. 2018). Given this, we plan to use 24 subjects (12 per dose sequence) which will have a power of 80% to detect an effect size of 1.20 standard deviations for changes in AHI, OSA-18 total score and arousal index, respectively, based on a two-sided test with  $\alpha=0.05$ . We estimate a 10% attrition rate for the study and, therefore, will recruit a total of 27 participants.

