## 9.4 Primary and Secondary Analyses

Below is a summary of planned statistical analyses of the primary, secondary and exploratory endpoints.

For the primary outcome, each participant's changes in obstructive AHI from baseline will be derived for both periods (high dose ato-oxy and low dose ato-oxy). To account for the features of a 2 by 2 crossover design, a linear mixed effects model with a subject random effect and a dose sequence indicator (e.g. high dose ato-oxy → low dose ato-oxy sequence indicator), a period indicator (e.g. 2nd period indicator) and a high dose ato-oxy dose indicator as the covariates will be fitted to the changes in obstructive AHI. This model will allow us to evaluate the effect of high dose ato-oxy on changes in obstructive AHI compared with the effect of low dose ato-oxy (primary analysis) while accounting for the potential carry-over, period and subject effects. In addition, it will also allow us to evaluate whether the overall mean change from baseline is different from zero by testing the intercept of the model and whether the carry-over or period effect exists by testing the regression coefficient estimate for the treatment sequence indicator and the period indicator, respectively (secondary analysis). Prior research has shown that obstructive AHI is likely to be not normally distributed. Therefore, a suitable transformation will be sought and applied to changes in AHI before the mixed effects model is fitted if necessary.

For health-related quality of life aims, a similar statistical analysis plan will be implemented. Specifically, a linear mixed effects model with a subject random effect and a treatment sequence indicator (e.g. high dose ato-oxy → low dose ato-oxy sequence indicator), a period indicator (e.g. 2nd period indicator) and a high dose ato-oxy dose indicator as the covariates will be fitted to the changes in OSA-18 (secondary outcome), PedsQL and Caregiver global impression of change (exploratory outcomes), respectively. If necessary, a suitable transformation will be sought and applied to changes in these measures, although prior research has shown that OSA-18 is normally distributed (Jung, Kim et al. 2011).

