For sleep architecture outcomes, we will again use a similar statistical analysis plan. Specifically, a linear mixed effects model with a subject random effect and a treatment sequence indicator (e.g. high dose ato-oxy → low dose ato-oxy sequence indicator), a period indicator (e.g. 2nd period indicator) and a high dose ato-oxy dose indicator as the covariates will be fitted to the changes in arousal index (secondary outcome) and percentage of N1, N3 and REM sleep (exploratory outcomes), respectively. For all aims, due to the cross-over design of the study, baseline covariates such as age, gender, baseline oAHI, etc. will not be included in the model as this would potentially create cross-over bias. (Kenward and Roger 2010, Mehrotra 2014).

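### Section 9.4 would transform the change in AHI rather than AHI itself; a nonlinear transform of the change leaves the shared baseline in the dose contrast

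*Combined protocol and SAP*

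**What the plan says.** Section 9.4 derives a change from baseline in oAHI for each child in each period. It fits a linear mixed model with a subject random effect and sequence, period and dose terms. The section then notes: "Prior research has shown that obstructive AHI is likely to be not normally distributed". Its remedy is that "a suitable transformation will be sought and applied to changes in AHI before the mixed effects model is fitted if necessary". The quality-of-life measures get matching wording: "If necessary, a suitable transformation will be sought and applied to changes in these measures". No function is named, no test or threshold defines necessity, and the timing relative to unblinding is not stated.

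Three other statements bear on this:

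- **Section 4.1:** "the screening PSG night will serve as the baseline measure for apnea hypopnea index (AHI) and other PSG endpoints". There is one baseline per child, and both periods use it.
- **Section 9.4, end:** "baseline covariates such as age, gender, baseline oAHI, etc. will not be included in the model". No model term would absorb baseline if it stayed in the response.
- **Section 5.2:** the exclusion "Absence of OSA defined as total AHI <5" sets a lower limit on severity and no upper one, so baselines can differ widely.

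**The concern.** The reason given for transforming is the distribution of oAHI itself, yet the operation is applied to the difference. In a crossover with a single shared baseline, these are not interchangeable. Transforming the value and then differencing keeps the comparison within the child and free of baseline. Transforming the difference makes the size of a child's dose contrast depend on how far the on-drug values lie from one pre-treatment night.

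This clause governs the primary test. If it is used, the estimate is a difference of transformed changes, weighted by baseline severity. It reads neither in events per hour nor as a ratio. Under a proportional dose effect, it can also lose power against the simple alternative.

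**Working it through.** **The plan's own figure.** Section 9.2 claims "power of 80% to detect an effect size of 1.20 standard deviations for changes in AHI" with 12 children per sequence and two-sided alpha 0.05. Two-sample t test, df = 22, noncentrality 1.20 × √(12/2) = 2.94: power 0.802, which reproduces the stated 80%. For attrition, 24/0.90 = 26.7, rounded up to 27. Section 9.2 does not say whether the 1.20 SD refers to a raw or a transformed scale.

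**Algebra.** Let B be the shared baseline and H and L the on-drug values at high and low dose.

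- Raw change: (H − B) − (L − B) = H − L. B cancels.
- Transform, then difference: [g(H) − g(B)] − [g(L) − g(B)] = g(H) − g(L). B cancels.
- Transform the change: f(H − B) − f(L − B). Its derivative in B is f′(L − B) − f′(H − B), which is zero throughout only if f is linear.

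This needs no assumption about the data. It applies to children with both periods.

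**Worked example (illustrative values).** H = 4, L = 8 events/h:

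| Baseline | Changes (high, low) | Raw contrast | Cube root of change | Change in log(oAHI+1) |
|---|---|---|---|---|
| 10 | −6, −2 | −4 | −1.82 + 1.26 = −0.56 | ln(5/9) = −0.59 |
| 20 | −16, −12 | −4 | −2.52 + 2.29 = −0.23 | −0.59 |
| 40 | −36, −32 | −4 | −3.30 + 3.17 = −0.13 | −0.59 |

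The cube-root contrast varies about 4-fold (0.56/0.13 = 4.3) with identical on-drug values. A second pair (H = 5, L = 10; baselines 12, 20, 40) gives −0.653, −0.312, −0.164, again a 4-fold spread.

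**Effect of baseline noise on the test.** In one simulated data set of 24 children, the on-drug values were held fixed and only the baseline noise was redrawn. The p-value did not move for raw change (0.0057) or for log-then-difference (0.0006). For cube root of change its central 95% range was 0.001 to 0.157.

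**Power.** The documents give no paediatric variance or dose ratio, so every input here is assumed: 12 per sequence, lognormal oAHI, entry at baseline 5 or more. Necessity is taken as Shapiro-Wilk p < 0.05 on the changes, also an assumption. Two rules were compared. If triggered, one takes the cube root of the change and the other takes the change in log(oAHI+1). Both use raw change otherwise.

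- Proportional dose effect, four scenarios: log-then-difference gained 13 to 21 points of power.
- Additive dose effect, two scenarios: the rules differed by less than 1 point, because the trigger seldom fires.
- No dose effect: rejection stayed near 5%.

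**The case against.** The clause is conditional, and that limits the harm considerably. With the same assumed trigger, it fires in only 5 to 13% of trials under an additive effect, and the rule then costs 0.3 to 2.2 points against raw change. Under a proportional effect, the cube-root rule ranges from 9 points below raw change to 6 above (mean −2.3), and the asinh rule from 6 below to 6 above (mean −0.3). So against untransformed change the clause costs little on average. The sizeable loss appears only against log-then-difference. This stands.

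A reader might infer more than the documents support:

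- **A 12-fold distortion.** That figure appears if baseline 8 is added to the example (−1.59 against −0.13). There the low-dose change is exactly zero, where the cube root has infinite slope. It is not representative.
- **Inflated type I error.** A fixed trigger rule with cube root or asinh rejected in 3.8 to 5.1% of null trials. Taking the best p-value over raw change and three transformed changes gave 7.6%, but nothing in the plan says the scale would be picked on treatment results. Section 9.4 places the transformation before model fitting, and Section 6.3 keeps investigators blinded. The plan lacks an explicit lock before unblinding; that is a gap, not evidence of inflation.
- **A contradiction with the exclusion of baseline covariates.** Section 9.4 gives cross-over bias as its reason for that exclusion. Transforming the response adds no covariate, so the two statements do not conflict.
- **Unstable conclusions peculiar to this clause.** Raw and cube-root analyses disagree on p < 0.05 in 14 to 25% of simulated trials, but raw and log(oAHI+1) disagree in 6 to 32%. That is ordinary sensitivity to scale.

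A log scale also departs from the raw-change null hypothesis in Section 9.1 ("no difference in change from baseline in obstructive AHI in the high dose ato-oxy study period"). That is true, but its contrast remains a within-child comparison of the two doses, free of baseline.

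**Conclusion.** The point holds in limited form. Section 9.4 names an inferior operation; this is more than a missing detail. For children with both periods, a nonlinear transform of the change leaves the shared baseline in the primary contrast, while raw change and transform-then-difference remove it. That conclusion is algebraic. Its size in the example is about 4-fold over baselines of 10 to 40.

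The consequence arises only if the clause is used, and it concerns what is estimated, how children are weighted, and power. The 13 to 21 point power difference rests wholly on assumed variances, effects and trigger, and applies only to a proportional effect.

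Two limits remain. The mITT definition in Section 9.3 admits children with one primary measurement. For them exact cancellation is unavailable on any of these scales. And nothing here shows that the plan must commit outright to raw change or to log. With 72 assumed scenarios, log was 5 to 27 points more powerful than raw under proportional effects and 4 to 22 points less under additive ones, so that choice is the sponsor's trade-off.

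**What to change.** In Section 9.4, replace the clause with:

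> If a transformation is needed, it will be applied to the obstructive AHI values (log(oAHI+1)) before the change from baseline is computed, never to the change itself. The decision will be made on blinded pooled data before unblinding, and the untransformed-change analysis will also be reported.

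Apply the same order of operations to the other measures in Section 9.4 that have a baseline value. State the criterion for needing a transformation in the same place.

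**Cost.** One clause is rewritten, with no new data or visits. The sample size stays at 24 evaluable and 27 recruited, provided 1.20 SD is the target on whichever scale is used. If the transformation is triggered, the result reads as a ratio of (oAHI+1), not of oAHI, and depends on a conventional offset. For 4 against 8 events/h the ratio is 4.5/8.5 = 0.53, 5/9 = 0.56 or 6/10 = 0.60 with offsets of 0.5, 1 or 2. Reporting the untransformed change alongside keeps a result in events per hour.

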**Overall Design:**

This is a randomized, double blind, cross-over study of the combination of atomoxetine and oxybutynin (ato-oxy) in children with DS and OSA documented by polysomnography (PSG). Participants will receive high dose ato-oxy for four weeks as well as low dose ato-oxy for four weeks in random order. During the high dose ato-oxy period, participants will take 5 mg oxybutynin and 0.5mg/kg/day (max 40 mg) atomoxetine nightly for one week. Atomoxetine dose will then be increased to 1.2 mg/kg/day (max 80 mg). During the low dose ato-oxy period, participants will take 5 mg oxybutynin and 0.5mg/kg/day (max 40 mg) atomoxetine. Dosing of the study treatment will occur approximately 30 minutes prior to bedtime. Participants who withdraw from the study will not be replaced.

Study participants will undergo eligibility screening that will include an initial screening to determine whether non- PSG enrollment criteria are met, followed by a 1-night in-lab PSG and health-related quality of life assessment for participants who qualify based on non-PSG criteria. For participants who are eligible and enroll in the study, the screening PSG night will serve as the baseline measure for apnea-hypopnea index (AHI) and other PSG endpoints. On the final night of dosing for both high dose ato-oxy and low-dose ato-oxy, participants will return for inpatient PSG and health-related quality of life assessment. The primary efficacy endpoint is the change in obstructive AHI from baseline (high dose ato-oxy vs. low dose ato-oxy).

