## 6.3 Measures to Minimize Bias: Randomization and Blinding

All participants (if AHI >5 on screening PSG) will be randomized to receive both high dose ato-oxy and low dose ato-oxy in random order. Each participant will be assigned a unique number

(randomization number) that encodes the participant's assignment to 1 of the 2 treatment orders of the study, according to the randomization schedule generated using a validated computer program.

Study treatment will be dispensed after PSG screening, as summarized in Section 1.3.

Returned study treatment should not be redispensed to the participants.

In case of an emergency, the Investigator has the sole responsibility for determining if unblinding of a participant's study treatment assignment is warranted. Participant safety must always be the first consideration in making such a determination. If a participant's study treatment assignment is unblinded, the DSMB must be notified within 24 hours after breaking the blind. The date and reason that the blind was broken must be recorded in the source documentation and electronic case report form (eCRF), as applicable.

Participants will be randomly assigned in a 1:1 equal allocation ratio (stratified by age 6-12 and 13-17) to receive 1 of 2 different study treatment orders, using permuted blocked randomization. Investigators will remain blinded to each participant's assigned study treatment throughout the study.

In the event of a Quality Assurance audit, the auditor(s) will be allowed access to unblinded study treatment records at the site(s) to verify that randomization/dispensing has been done accurately.

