### 9.3 Populations for Analyses

For the purposes of analysis, the following analysis sets are defined:

Population	Description
Enrolled	All participants who signed the ICF (including screening failures).
Modified Intent to Treat (mITT) Population	The mITT Population comprises all participants who are randomized, take at least 1 dose of any of the study treatments, and have at least 1 measurement on the primary endpoint. Participants will be analyzed for efficacy according to the treatment group into which they are randomized.
Safety Population	The Safety Population consists of all participants who are randomized and receive at least 1 dose of any of the study treatments. Participants will be analyzed for safety based on the treatment received.
Per Protocol (PP) Population	The PP Population consists of all participants without any major protocol violations that could influence efficacy assessment, and who are at least 80% compliant with the study medication. Participants in this population will be analyzed according to the treatment they actually received.

The primary endpoint comparison between the high dose ato-oxy and low dose ato-oxy will consider all mITT participants randomized to those 2 groups.

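### Section 9.4 bars baseline covariates for a reason that does not fit one shared baseline; the dose contrast is unaffected, and the cost falls on the sequence (carry-over) test

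*Combined protocol and SAP*

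**What the plan says.** The primary analysis in Section 9.4 is "a linear mixed effects model with a subject random effect and a dose sequence indicator", a period indicator and a high-dose indicator, fitted to the change in obstructive AHI. The same form is used for the quality-of-life and sleep-architecture outcomes. As a secondary analysis the section plans to test "whether the carry-over or period effect exists by testing the regression coefficient estimate for the treatment sequence indicator and the period indicator", and to test the intercept as the overall mean change. It then rules out covariates for all aims: "baseline covariates such as age, gender, baseline oAHI, etc. will not be included in the model as this would potentially create cross-over bias". Two papers on crossover trials are cited, and no mechanism is described.

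On the baseline, the Synopsis (Overall Design) says that "the screening PSG night will serve as the baseline measure for apnea-hypopnea index (AHI) and other PSG endpoints". Table 1 places PSG and questionnaires at Visits 1, 2 and 3 only, so nothing is measured after washout and before the second period.

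On allocation, Section 6.3 says: "Participants will be randomly assigned in a 1:1 equal allocation ratio (stratified by age 6-12 and 13-17") to one of two treatment orders. The mITT set in Section 9.3 admits children who "have at least 1 measurement on the primary endpoint", so a child with one period can enter the analysis.

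**The concern.** The reason given for the bar is bias. Mixing within-child and between-child information through a covariate requires the covariate to differ between a child's two periods. Here the baseline, age and gender do not differ. If the reason does not apply, the plan gives up collected information, and leaves out its own stratification factor, for nothing.

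What is at stake is limited. The sequence test compares two groups of about 12 children, and its outcome is a change score that carries baseline variation directly. Low precision there makes a non-significant carry-over result hard to interpret. Section 9.4 also tests the intercept, which is likewise not a within-child quantity.

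**Working it through.** **Inputs from the documents.** 24 evaluable children, 12 per sequence; effect size 1.20 SD; two-sided alpha 0.05; 80% power; 10% attrition, 27 recruited (Section 9.2). One baseline per child (Synopsis, Table 1). **Assumed, because the documents do not give it:** the correlation rho between baseline and on-treatment AHI, taken as 0.3 to 0.9, with equal variances and equal correlations.

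**1. The plan's own figure.** Section 9.2 says that the comparison is "reduced to a two-sample t test with a common variance of" σ²/2. A noncentral t calculation with 12 per group, d = 1.20 and 22 degrees of freedom gives 80.2% power, and 24/0.90 = 26.7 rounds up to 27. The figure is reproduced when 1.20 is in units of σ/√2.

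**2. The dose contrast.** Write the change for child i in period p as

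D_ip = μ + λ·seq_i + π·per_p + τ·high_ip + β·B_i + γ·age_i + u_i + e_ip.

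In the half-difference (D_i1 − D_i2)/2 the terms μ, λ, β, γ and u all cancel. Its mean is (−π + τ)/2 in the high-then-low sequence and (−π − τ)/2 in the other, so the difference between sequences is τ. Its variance is 2σ²/4 = σ²/2, the reduction that Section 9.2 uses. Baseline and age do not appear in it.

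Numerical check by REML on simulated data with 12 + 12 complete pairs: dose estimate −2.56478 (SE 1.10474) without covariates, and −2.56478 (SE 1.10474) with baseline and age. In a second set of fits the estimate moved by at most 2e-15, and the model SE was 0.203 against 0.202.

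**3. The sequence contrast.** This compares the two sequences on each child's mean change. With unit variances:

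- unadjusted variance: (1+rho)/2 + 1 − 2·rho = 1.5(1−rho)
- adjusted for baseline: (1+rho)/2 − rho² = (1−rho)(1+2·rho)/2
- ratio: (1+2·rho)/3

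| rho | variance ratio | SE ratio (square root) | power, if unadjusted is about 80% |
|---|---|---|---|
| 0.3 | 0.53 | 0.73 | 96% |
| 0.5 | 0.67 | 0.82 | 92% |
| 0.7 | 0.80 | 0.89 | 86% |
| 0.9 | 0.93 | 0.97 | 81% |

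Adding age alone, when age does not predict change, leaves power at about 80%.

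**4. Skewed AHI.** Assumed: median baseline 12 to 20 events/h, log-SD 0.5 to 0.8, drug effects of 10% to 60% reduction, night-to-night log-SD 0.35, observed baseline at least 5, and 4,000 trials of 24 children per setting. On raw change, the SD of the sequence contrast fell from 3.06 to 1.85, 4.44 to 2.66, 8.83 to 4.05, and 4.35 to 3.56. The ratios are 0.60, 0.60, 0.46 and 0.82. Rejection under no carry-over was 3.8–4.4% without baseline and 4.3–4.9% with it. Further runs over similar settings, some with added between-child variation in response, widen the raw-change range to roughly 0.4 to 0.9. On log-ratio change the ratios were 0.92 to 1.01.

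**5. One-period children.** Assumed: 27 children, 3 lost after period 1, rho 0.5, true effect −0.60, 4,000 runs, simulation error about 0.003.

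| Loss after period 1 | mean estimate, no covariate | mean estimate, with baseline |
|---|---|---|
| unrelated to baseline | −0.601 | −0.601 |
| related to baseline, both sequences | −0.598 | −0.599 |
| related to baseline, one sequence only | −0.627 | −0.599 |

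In single data sets with 3 of 27 lost, the two estimates differed by a median of 0.014 SD and at most 0.087 SD.

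**The case against.** The strongest reply is that the bar costs the trial nothing that counts. The dose contrast is the same either way, for every outcome with complete pairs. The sequence test is secondary, and no decision hangs on it: there is no two-stage rule, and period 2 is never discarded. Leaving covariates out would then be a legitimate choice with a badly worded reason. This stands as far as the primary result goes. It does not rescue the reason, and it does not justify running a planned test with less precision than the collected data allow.

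The size of the gain is also open to challenge. Section 9.4 expects non-normal AHI and allows a transformation of the changes. Log-ratio change is one candidate, and on that scale the gain nearly vanishes. This stands in full, so the raw-change range must not be quoted alone.

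Third, age is not shown to predict change, so its inclusion reflects the design and promises no precision. This too stands.

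A reader might infer that the bar biases or underpowers the primary comparison, or that adding covariates would strengthen it. The algebra rules out both for complete pairs. A reader might also infer that the protocol misreads the two papers that it cites. Their content was not available, so nothing is claimed about them. The argument rests on the design alone.

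**Conclusion.** The stated reason is wrong for this design. With one pre-randomisation baseline per child and complete pairs, a child-level covariate cannot bias the dose contrast. The primary estimate, its standard error, the sample size and the power are essentially unaffected whether or not covariates are added.

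The loss is confined to between-child quantities and to one-period mITT children. For the obstructive AHI sequence test it may be large on raw change (adjusted SE roughly 0.4 to 0.9 of unadjusted) and is small on a log-ratio scale (gain of about 0 to 8%). Both ranges rest on assumed variances, correlations and drug effects. A similar gain for OSA-18, arousal index or the exploratory outcomes is plausible but was not simulated. With one-period children, omitting baseline produced a small bias only where loss depended on baseline in one sequence alone, and the documents give no reason to expect that pattern. This is a correction to the analysis plan and does not put the primary result in doubt.

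**What to change.** In Section 9.4, delete the sentence that attributes bias to baseline covariates. Keep dose, period and sequence as they are, and prespecify two child-level covariates:

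- **The baseline of the same outcome**, centred at the trial mean and on the same scale as the analysed outcome (for example, log baseline if log-ratio change is analysed). Include it only where a baseline exists. Section 8.1.1 gives the Caregiver Global Impression of Change only at the end of each period, so that model takes no baseline term. Footnote 7 of Table 1 lists the scale with the questionnaires marked for Visit 1, and the two places should be reconciled.
- **The age stratum** (6–12 vs 13–17), centred or effect-coded.

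Centring both matters because the intercept is tested. Otherwise it would refer to a baseline of zero or to one age group, and not to the trial population as a whole.

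The cost is SAP wording and two between-child degrees of freedom (24 − 2 = 22 becomes 24 − 4 = 20), with none taken from the within-child dose contrast. No new data are needed. If the sponsor prefers the simpler primary model, the text should say that covariates are omitted because the within-child contrast does not need them, and the adjusted model should be prespecified for the sequence and intercept tests.
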